4.3 Selection of Study Population

This will be a single site study conducted at the Mirpur field site by the icddr,b. The first part (Part A) will enroll a total of 45 adult participants (30 vaccinees and 15 placebos) into one Cohort. The second part (Part B) will enroll a total of 150 toddlers (24-29 months) into 6 separate cohorts to be recruited in step-wise

fashion. Each cohort will enroll 25 toddlers (15 vaccinees and 10 placebos). The third part (Part C) will enroll a total of 100 younger children (12-23 months) into 4 separate cohorts in a step-wise fashion. Each cohort will enroll 25 younger children (15 vaccinees and 10 placebos). The fourth part (Part D) will enroll a total of 200 infants (6-11 months) into 5 separate cohorts to be recruited in a step-wise fashion. Each cohort will enroll 40 infants (30 vaccinees and 10 placebos). Toddlers, younger children and infants will only be enrolled if their parents are fully informed about the study and provide consent for their child's participation.

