4.4.2 Method of Assigning Participants to Treatment Groups (Randomization)

The randomization scheme will be generated and maintained by the Statistical Data Coordinating Center (SDCC) at the Emmes Corporation, Rockville, MD. Randomization will occur manually on the day participants are to receive their first study vaccination, after confirmation of eligibility and immediately prior to immunization. The unblinded study pharmacist or member of the IP formulation team will be provided with the treatment assignment codes for preparation of the vaccine or placebo to be given to each participant. The unblinded study pharmacist (or designee) will maintain the treatment code list in a secure place. Each participant's treatment assignment will be entered into the AdvantageEDCSM system at Emmes after product administration has occurred.

Eligible participants were randomized and assigned as shown below. The doses shown in **bold** are the highest safe doses chosen by the IPST. Where appropriate, all tables and figures will report the actual dose received.

- Part A: Adults 1:1:1 ratio Cohort A1
 - Full dose ETVAX only
 - Full dose ETVAX + 10 μg dmLT
 - o Placebo
- Part B: toddlers aged 24 59 months,
 - o Cohort B1 3:2 ratio
 - 1/4 dose ETVAX only
 - Placebo

- o Cohort B2 3:2 ratio
 - 1/2 dose ETVAX only
 - Placebo
- Cohort B3 3:2 ratio
 - Full dose ETVAX only
 - Placebo
- o Cohort B4 3:2 ratio
 - Highest safe dose ETVAX (1/2 dose) + 2.5μg dmLT
 - Placebo
- Cohort B5 3:2 ratio
 - Highest safe dose ETVAX (1/2 dose) + 5μg dmLT
 - Placebo
- Cohort B6 3:2 ratio
 - Highest safe dose ETVAX (1/2 dose) + 10μg dmLT
 - Placebo
- Part C: younger children aged 12 23 months,
 - o Cohort C1 3:2 ratio
 - 1/4 dose ETVAX only
 - Placebo
 - o Cohort C2 3:2 ratio
 - 1/2 dose ETVAX only
 - Placebo
 - Cohort C3 3:2 ratio
 - Highest safe dose ETVAX (1/2 dose) + 2.5µg dmLT
 - Placebo
 - o Cohort C4 3:2 ratio
 - Highest safe dose ETVAX (1/2 dose) + 5µg dmLT
 - Placebo
- Part D: infants aged 6 11 months,
 - Cohort D1 3:1 ratio
 - 1/8 dose ETVAX only
 - Placebo
 - O Cohort D2 3:1 ratio
 - 1/4 dose ETVAX only
 - Placebo
 - o Cohort D3 3:1 ratio
 - 1/2 dose ETVAX only
 - Placebo
 - O Cohort D4 3:1 ratio
 - Highest safe dose ETVAX (1/4 dose) + 2.5μg dmLT
 - Placebo
 - o Cohort D5 3:1 ratio
 - Highest safe dose ETVAX (1/4 dose) + 5µg dmLT
 - Placebo

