8 IMMUNOGENICITY EVALUATION

The secondary and exploratory immunogenicity analyses are based on the ALS assay, ELISA assay and fecal assays. Whole blood and plasma specimens will be collected for immunogenicity assessments at Screening, Day 7 and Day 19. Fecal specimens will be collected for immunogenicity assessments at Screening, Day 1, Day 7, Day 19 and Day 29. All immunogenicity analyses will be conducted using the FA and the PP populations, unless they are the same. The number of participants in a population may vary by antigen and assay type as only participants contributing assessments will be included in the population for a specific antigen and assay. Individual participant data listings of immunogenicity will be presented in Listings 16.2.6.1(a)(b)(c)(d) - 16.2.6.3(a)(b)(c)(d) for ALS, fecal, and plasma, respectively.

Pairwise comparisons between each dose of the vaccine without dmLT, and each vaccine co-administered with dmLT adjuvant dose and placebo will be performed for each age-group: adults, toddlers (24-59 months), younger children (12-23 months), and infants (6-11 months). In addition, pairwise comparisons will be made between the combined vaccine without dmLT group and the combined vaccine with dmLT as well as comparisons of these two group with placebo.

Due to the hypothesis generating nature of multiple statistical comparisons for immunogenicity associated with multiple endpoints for this age and dose escalating study, all estimations will be carried out using a two-sided 5% Type I error rate. For each immunogenicity endpoint and antigen analyzed, a Holm's-Bonferroni correction will be applied to determine significance.

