9.1.1 Solicited Events and Symptoms

Solicited adverse events will be collected pre-vaccination, 60 minutes post-vaccination and then daily for 7 days after vaccination and graded on a scale of 0 (absent), 1 (mild), 2 (moderate) and 3 (severe). Solicited events include: elevated oral temperature, nausea, vomiting, loose stools, diarrhea, abdominal pain/stomach ache, and acute systemic allergic reaction. Adults will have all events collected. Toddlers (24 - 59 months) will have all events except nausea collected and Younger Children (12 - 23 Months) and Infants (6 - 11 months) will only have oral temperature, vomiting, loose stools, diarrhea and acute systemic allergic reaction collected.

The proportion of participants reporting at least one solicited adverse event within 7 days of any vaccination will be summarized for each solicited adverse event and for any solicited adverse event. The 95% CI calculated using Clopper-Pearson methodology from a binomial distribution (SAS Proc Freq with a binomial option) will be presented (Tables 14.3.1.1(a)(b)(c)(d)).

For each solicited adverse event and for any solicited adverse event, the maximum severity over 7 days after each vaccination will be summarized for the Safety population. The number and percentage of participants reporting each event will be summarized for each treatment group by the maximum severity. For each event the denominator is the number of participants with non-missing data for the specific event (Tables 14.3.1.2(a)(b)(c)(d)).

The number and percentage of participants reporting any solicited adverse event and reporting each individual solicited adverse event will be summarized for each day post vaccination for each vaccination by Treatment group (Tables 14.3.1.3(a)(b)(c)(d)) and severity. The percent of participants reporting any solicited event will be displayed graphically in a bar chart in Figures 14.3.1.4(a)(b)(c)(d)).

Fisher's exact test will be used to compare the proportion of participants with solicited reactogenicity events between each of the vaccine arms with the placebo arms. In addition, the vaccine arms without dmLT will be combined, the vaccine arms with dmLT will be combined and all vaccine arms will be combined and each will be compared to placebo. The results will be summarized in Tables 14.3.1.5(a)(b)(c)(d).

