A logistic regression analysis will be presented to look at the proportion of vomiting after any ETVAX dose, with covariates for sex, age group (i.e., cohort's B, C and D), dose and adjuvant in the model. The age group categories will correspond with cohorts B, C and D: 6-11 months, 12-23 months, and 24-59 months, respectively. Results will be summarized for all vaccinated children in Table 14.3.1.6.1 and all children in Table 14.3.1.6.2.

The primary purpose of the statistical comparisons is to screen out potential solicited reactogenicity events that need further clinical evaluation. Therefore, they are not considered formal statistical hypothesis tests and it is acknowledged that there will be inflated Type I errors (i.e., inflated false statistical significances) from performing multiple unadjusted comparisons.

Solicited adverse events by participant will be presented in Listings 16.2.7.1(a)(b)(c)(d).

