Symptom	n	%	n	%	P-value ^a	n	%	P-value ^a
Any Symptom	XX	XX.X	xx	XX.X	0.xxx	XX	XX.X	0.xxx
Elevated Oral Temperature	xx	XX.X	XX	XX.X	0.xxx	xx	xx.x	0.xxx
Nausea	XX	XX.X	xx	XX.X	0.xxx	XX	XX.X	0.xxx
Vomiting	XX	XX.X	xx	XX.X	0.xxx	XX	XX.X	0.xxx
Loose stools	xx	XX.X	XX	XX.X	0.xxx	xx	xx.x	0.xxx
Diarrhea	XX	xx.x	XX	XX.X	0.xxx	XX	XX.X	0.xxx
Abdominal pain/stomach ache	xx	XX.X	XX	XX.X	0.xxx	XX	xx.x	0.xxx
Acute systemic allergic reaction	XX	xx.x	XX	XX.X	0.xxx	XX	XX.X	0.xxx

N = Number of participants in the Safety population; n = Number of participants with a symptom reported post-vaccination.

^a P-value is from a Fisher's exact test, testing the treatment vs placebo.

TABLE 14.3.1.5b: Comparison of the Proportion of Participants Experiencing Solicited Events by Treatment Group - Toddlers (24 - 59 Months)

		ecebo =XX)	E	TVAX 1 (N=X	/4 Dose XX)	E	TVAX 1/ (N=X		ET	VAX F (N=X	'ull Dose XX)		mbined l	ETVAX =XX)
Symptom	n	%	n	%	P-value ^a	n	%	P-value ^a	n	%	P-value ^a	n	%	P-value ^a
Any Symptom	XX	XX.X	XX	xx.x	0.xxx	XX	XX.X	0.xxx	XX	xx.x	0.xxx	XX	XX.X	0.xxx
Elevated Oral Temperature	XX	XX.X	XX	xx.x	0.xxx	XX	XX.X	0.xxx	XX	xx.x	0.xxx	XX	XX.X	0.xxx
Vomiting	XX	XX.X	XX	xx.x	0.xxx	XX	XX.X	0.xxx	XX	XX.X	0.xxx	XX	XX.X	0.xxx
Loose stools	XX	XX.X	XX	xx.x	0.xxx	XX	XX.X	0.xxx	XX	XX.X	0.xxx	XX	XX.X	0.xxx
Diarrhea	XX	XX.X	XX	XX.X	0.xxx	XX	XX.X	0.xxx	XX	XX.X	0.xxx	XX	XX.X	0.xxx
Abdominal pain/stomach ache	XX	XX.X	XX	xx.x	0.xxx	XX	XX.X	0.xxx	XX	XX.X	0.xxx	XX	XX.X	0.xxx
Acute systemic allergic reaction	XX	XX.X	XX	XX.X	0.xxx	XX	XX.X	0.xxx	XX	XX.X	0.xxx	XX	XX.X	0.xxx

	` `	ETV. shest sat 2.5 µg d (N=)	fe dose) + lmLT	(hig	ETVA shest safe 5 µg dn (N=X	e dose) + nLT	` 0	ETV hest sat 10 µg d (N=)	fe dose) + lmLT	Co	ombined l + dml (N=X)	LT
Symptom	n	%	P-value ^a	n	%	P-value ^a	n	%	P-value ^a	n	%	P-value ^a
Any Symptom	XX	XX.X	0.xxx	XX	XX.X	0.xxx	XX	XX.X	0.xxx	XX	XX.X	0.xxx
Elevated Oral Temperature	XX	XX.X	0.xxx	XX	XX.X	0.xxx	XX	XX.X	0.xxx	XX	XX.X	0.xxx
Vomiting	XX	XX.X	0.xxx	XX	XX.X	0.xxx	XX	XX.X	0.xxx	XX	XX.X	0.xxx
Loose stools	XX	XX.X	0.xxx	XX	XX.X	0.xxx	XX	XX.X	0.xxx	XX	XX.X	0.xxx
Diarrhea	XX	XX.X	0.xxx	XX	XX.X	0.xxx	XX	xx.x	0.xxx	XX	xx.x	0.xxx
Abdominal pain/stomach ache	XX	xx.x	0.xxx	XX	XX.X	0.xxx	XX	xx.x	0.xxx	XX	XX.X	0.xxx
Acute systemic allergic reaction	xx	xx.x	0.xxx	XX	XX.X	0.xxx	XX	xx.x	0.xxx	XX	XX.X	0.xxx

N = Number of participants in the Safety population; n = Number of participants with a symptom reported post-vaccination.

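### The placebo comparisons of solicited events report only a p-value and warn only of false positives, though single-arm power is low; a risk difference with a 95% CI should be added

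*SAP*

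**What the plan says.** Vaccine-induced reactogenicity is one of the primary endpoints (SAP Section 3.2.1). Section 9.1.1 plans the comparison: "Fisher's exact test will be used to compare the proportion of participants with solicited reactogenicity events", each vaccine arm against placebo. It also plans to compare the combined arms without dmLT, the combined arms with dmLT, and all vaccine arms together with placebo. The stated purpose is: "The primary purpose of the statistical comparisons is to screen out potential solicited reactogenicity events that need further clinical evaluation". On error rates it says that "they are not considered formal statistical hypothesis tests and it is acknowledged that there will be inflated Type I errors". It says nothing about power and sets no significance level for these tests.

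The shells for Tables 14.3.1.5a-d give n and % per group and a p-value, with the footnote: "P-value is from a Fisher's exact test, testing the treatment vs placebo". They have no column for the difference or its interval.

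Other safety output is planned. Section 9.1.1 has per-arm rates with Clopper-Pearson intervals, maximum severity, by-day tables, bar charts, listings, and a logistic model for vomiting in children that includes an ETVAX-versus-placebo odds ratio (Table 14.3.1.6.2). Section 6.6.1 has the Independent Protocol Safety Team (IPST) review each cohort and the DSMB meet before each age step. Section 6.6.2 has pause rules based on counts of severe related events.

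**The concern.** The comparison with placebo separates vaccine reactions from background illness, and it is the analysis that Section 9.1.1 uses to pick out events for a closer look. In a safety screen with 15 to 30 vaccinees per arm, the more likely error is to miss a real excess. The text guards only against the opposite error.

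A table of p-values cannot tell a reader whether a non-significant row reflects similar rates or too few participants. The per-arm intervals of Table 14.3.1.1 do not answer this either, because each describes one arm and none describes the excess over placebo. At stake is how the tolerability results of a primary endpoint can be read in the study report.

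**Working it through.** **The plan's own safety sizing.** Section 5 considers one arm at a time. The chance of at least one event is 1 − (1 − p)^n, and the one-sided 95% upper bound after zero events is 1 − 0.05^(1/n).
- n = 15: 1 − 0.897^15 = 80.4%; 1 − 0.857^15 = 90.1%; bound 18.1%.
- n = 30: 1 − 0.947^30 = 80.5%; 1 − 0.926^30 = 90.0%; bound 9.5%.

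These agree with the stated figures. Section 5 gives no power for a comparison with placebo.

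**Inputs from the document (Sections 4.3 and 4.4.2).**
- Adults: "The first part (Part A) will enroll a total of 45 adult participants (30 vaccinees and 15 placebos) into one Cohort" and "Part A: Adults 1:1:1 ratio Cohort A1", so 15 vs 15.
- Toddlers: "Each cohort will enroll 25 toddlers (15 vaccinees and 10 placebos"; six cohorts give 6 × 10 = 60 placebo, so 15 vs 60.
- Younger children: 15 vaccinees and 10 placebo in each of four cohorts, so 15 vs 40.
- Infants: 30 vaccinees and 10 placebo in each of five cohorts, so 30 vs 50.

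**Assumptions.**
- Placebo is pooled within age group, as the single placebo column of the shells implies.
- The level is two-sided 0.05. Section 8 sets this for immunogenicity ("all estimations will be carried out using a two-sided 5% Type I error rate"); Section 9.1.1 sets none.
- Event rates are 10% on placebo and 30% on vaccine. The document gives no reactogenicity rates.

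**Formula.** Power = Σ Bin(x; n_v, 0.30) · Bin(y; n_p, 0.10) over all tables (x, y) whose two-sided Fisher p is at most 0.05. The miss rate is 1 − power.

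| Comparison | Vaccine vs placebo | Missed |
|---|---|---|
| Adults, single arm | 15 vs 15 | 85% |
| Toddlers, single arm | 15 vs 60 | 56% |
| Younger children, single arm | 15 vs 40 | 64% |
| Infants, single arm | 30 vs 50 | 43% |
| Adults, all vaccine | 30 vs 15 | 75% |
| Toddlers, without dmLT or with dmLT | 45 vs 60 | 30% |
| Toddlers, all vaccine | 90 vs 60 | 17% |
| Younger children, without dmLT or with dmLT | 30 vs 40 | 47% |
| Younger children, all vaccine | 60 vs 40 | 35% |
| Infants, without dmLT | 90 vs 50 | 21% |
| Infants, with dmLT | 60 vs 50 | 28% |
| Infants, all vaccine | 150 vs 50 | 14% |

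These are planned sizes. The footnote to Table 14.3.1.6.1 puts the full-dose recipients at 5; at 5 vs 60 the miss rate is 80%.

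For a rise from 10% to 25%, single-arm power is 9% (adults), 30% (toddlers), 24% (younger children) and 38% (infants).

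**False positives per test.** With both rates at 10%, the single-arm tests reach p ≤ 0.05 in either direction in only 0.5% to 3.3% of trials. Each test is conservative. The inflation that Section 9.1.1 mentions comes from the number of tests.

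**What the p-value hides.** Take 3/15 vs 1/15.
- Fisher: four events among 30, with C(30,4) = 27,405. The upper tail is [C(15,3)·15 + C(15,4)] / 27,405 = (6,825 + 1,365) / 27,405 = 0.299. The distribution is symmetric, so two-sided p = 0.60.
- Difference: 0.200 − 0.067 = +13 points.
- Wilson limits are 0.071 to 0.452 for 3/15 and 0.012 to 0.298 for 1/15.
- Newcombe lower limit: 0.133 − √[(0.200 − 0.071)² + (0.298 − 0.067)²] = −0.13.
- Newcombe upper limit: 0.133 + √[(0.452 − 0.200)² + (0.067 − 0.012)²] = +0.39.

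The table would show p = 0.60. The interval shows that an excess of up to 39 points is not excluded.

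**The case against.** The strongest reply is that the plan does not depend on these p-values. The IPST reviews solicited symptoms after every cohort, and the DSMB meets before each age step. More than two participants in a cohort with the same severe related solicited event pauses vaccination without any test. Rates, severity, timing and individual events are all tabulated or listed. The SAP calls the comparisons informal and claims no power for them, and low between-arm power comes with arms of 15 to 30. The pooled comparisons do better, and the 10% and 30% rates are assumptions.

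Much of this stands. A reader might infer that events are selected for review by p-values alone, or that real harms will pass as no different from placebo. The document supports neither. It sets no 0.05 cut-off for the safety tests, nowhere equates non-significance with no difference, and provides the other reviews listed above. Nor do the single-arm miss rates describe the whole screen.

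The narrower point remains. The pause rules for adverse events short of death or an SAE cover only related events or laboratory values of grade 3 or higher. The odds ratios cover only vomiting in children. The pooled tests average over dose and adjuvant level, while Section 4.1 seeks safety and the best dose within each age group; in adults even the pooled test misses 75%. For the other solicited events, the p-value is the only planned between-group statistic.

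**Conclusion.** The concern holds as a reporting weakness in Section 9.1.1 and Tables 14.3.1.5a-d. Comparisons with a stated screening role carry no effect estimate or interval, and the accompanying caution covers only Type I error. For a 10% to 30% rise, single-arm tests miss 43% to 85% of the time; pooled tests miss 14% to 47% in children and 75% in adults. A non-significant row therefore says little about tolerability, especially for a single arm.

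The sizes rest on assumed rates, an assumed two-sided 0.05, planned enrolment and placebo pooled within age group. The absence of a difference and interval from the shells rests on none of these. The point does not show that safety oversight during the trial is inadequate.

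**What to change.** In Tables 14.3.1.5a-d, add for each single-arm and pooled comparison the risk difference versus placebo with a 95% CI, naming the method (for example Miettinen-Nurminen or Newcombe). The all-vaccine comparison planned in Section 9.1.1 has no column in these shells and needs one to carry its estimate. Note under the tables that the interval is not an inversion of Fisher's test, so the two can disagree: 4/15 vs 0/15 gives p = 0.10 with +27 points (Newcombe 95% CI +1 to +52).

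In Section 9.1.1, state that the individual comparisons have low power, that a non-significant p-value is not evidence of comparable tolerability, and that the upper confidence limit shows the excess not excluded.

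Set no numerical trigger for clinical review in the SAP; leave that to the safety team. A fixed excess of 10 points, for instance, would flag 8% to 17% of single-arm rows by chance with both rates at 10%.

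The cost is a few sentences and an added difference column per comparison in four shells, with no new data. Some intervals will be wide, which is the information the reader needs.

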9.1.2 Unsolicited Adverse Events

The proportion of participants reporting at least one unsolicited adverse event will be summarized by MedDRA system organ class and preferred term for each treatment group and overall. Denominators for percentages are the number of participants in the Safety population. A 95% CI calculated using Clopper-Pearson methodology from a binomial distribution (SAS Proc Freq with a binomial option) will be presented for each MedDRA system organ class and preferred term (Tables 14.3.1.7(a)(b)(c)(d))

Unsolicited adverse events by participant will be presented in Listings 16.2.7.2(a)(b)(c)(d).

The following summaries for unsolicited adverse events will be presented by treatment group:

- Participant level summary of maximum severity and relationship to study product by MedDRA SOC and PT (Tables 14.3.1.8.1(a)(b)(c)(d));
- Participant level summary of related unsolicited events by maximum severity, MedDRA SOC and PT (Tables 14.3.1.8.2(a)(b)(c)(d));
- Participant incidence of unsolicited adverse events over time by MedDRA SOC and PT (Days 1-8, Days > 8) (Tables 14.3.1.9.1(a)(b)(c)(d));
- Participant incidence of related unsolicited adverse events over time by MedDRA SOC and PT (Days 1-8, Days > 8) (Tables 14.3.1.9.2(a)(b)(c)(d));
- Total frequency of adverse events over time by MedDRA SOC and PT (Days 1-8, Days > 8) (Tables 14.3.1.10(a)(b)(c)(d));
- Participant listing of non-serious adverse events of moderate or greater severity (Tables 14.3.2.2(a)(b)(c)(d));
- Bar chart of the frequency of events for non-serious adverse events by maximum severity and MedDRA SOC (Figures 14.3.1.11(a)(b)(c)(d));
- Bar chart of the percent of participants reporting a non-serious adverse event by maximum severity and MedDRA SOC (Figures 14.3.1.12(a)(b)(c)(d));
- Bar chart of the frequency of any adverse event by maximum severity (Figures 14.3.1.13(a)(b)(c)(d));
- Bar chart of the percent of participants of any adverse event by maximum severity (Figures 14.3.1.14(a)(b)(c)(d));
- Bar chart of the frequency of non-serious adverse events by relationship to treatment and MedDRA SOC (Figures 14.3.1.15(a)(b)(c)(d));

- Bar chart of the percent of participants of non-serious adverse events by relationship to treatment and MedDRA SOC (Figures 14.3.1.16(a)(b)(c)(d));
- Bar chart of the frequency of any adverse event by relationship to treatment (Figures 14.3.1.17(a)(b)(c)(d)).
- Bar chart of the percent of participants experiencing any adverse event by relationship to treatment (Figures 14.3.1.18(a)(b)(c)(d)).

9.2 Deaths, Serious Adverse Events and other Significant Adverse Events

A listing of deaths and SAEs (Tables 14.3.2.1(a)(b)(c)(d)) will be presented including Participant ID, Age (years for adults and months for toddlers, younger children, and infants) Adverse Event Description, Adverse Event Onset Date/End Date, Last Days Post Dose, Reason Reported as an SAE, Relationship to Treatment, Outcome, and Duration of Event (days).

9.3 Pregnancies

If any adult participants in the Safety population become pregnant during the study, every attempt will be made to follow these participants to completion of pregnancy to document the outcome, including information regarding any complications with pregnancy and/or delivery. If more than 5 pregnancies are reported, a table summarizing the total pregnancies, number of live births, and number of spontaneous abortions, elective abortions or still births by treatment will be presented. In addition, a listing of all pregnancies and outcomes will be presented (Listing 16.2.11(a)).

9.4 Clinical Laboratory Evaluations

Safety clinical laboratory evaluations will be performed at Screening and at Day 7 at the designated site laboratory and will include: hemoglobin (HgB), white blood cells (WBC), platelet counts, neutrophils, lymphocytes, alanine transaminase (ALT), and creatinine. Albumin and total bilirubin will be collected at the Screening visit only. In addition, screening laboratory tests will include serum HCG pregnancy tests for females of childbearing potential only, and screening for HIV, HCV and HBV.

The summary tables will include all laboratories collected at Screening and Day 7 and which have toxicity grades. These include HGB, platelet counts, WBC, ALT, and creatinine. For each part, the distribution of laboratory results by severity, scheduled study day and treatment group will be presented in Tables 14.3.4.1(a)(b)(c)(d) for any laboratory parameter and each individual laboratory parameter. The observed and change from screening measurements will be summarized using descriptive statistics including mean, standard deviation, median, 25th and 75th percentiles, minimum and maximum values by scheduled study day, for each laboratory parameter in Tables 14.3.4.2(a)(b)(c)(d). Graphical presentation of changes in laboratory values will be presented using box plots as depicted in Figures 14.3.4.3(a)(b)(c)(d), for each laboratory parameter. Unscheduled or repeated follow-up tests for medical or safety reasons will be listed and included in the maximum post-baseline row on the summary tables, but will otherwise be excluded from tabular and graphical summaries.

Participant visits with abnormal laboratory results, Grade 1 severity or higher, will be presented in Tables 14.3.4.4(a)(b)(c)(d).

Listings of all individual clinical laboratory results will be provided by hematology, biochemistry and serology (Listings 16.2.8.1(a)(b)(c)(d)-16.2.8.3(a)(b)(c)(d), respectively). Results meeting the protocol defined toxicity of Grade 1 or higher will have their grade provided in parentheses after the result.

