4.5.1 Safety Variables

The safety variables to be assessed are adverse events (AEs), serious adverse events (SAEs), and multiple clinical safety laboratory measurements [including white blood cells (WBC), hemoglobin (Hgb), platelets, differentials (neutrophils and lymphocytes), alanine aminotransferase (ALT), albumin, total bilirubin and serum creatinine], physical exam, and vital sign parameters. Solicited systemic reactogenicity events within 7 days of each vaccination will be collected. If a solicited sign or symptom has started during the seven days post-vaccination and continues, it will continue to be reported as a reactogenicity symptom. Only when the reactogenicity event is considered an SAE, as defined below, will it be reported on an AE/SAE form in addition to the reactogenicity form. Any symptom starting after seven days post-vaccination will be recorded as an AE. Unsolicited AEs will be collected through the Day 42 visit. SAEs will be collected through six months after the first vaccination or the duration of the study.

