Programming Note: Use the same Table shell as Table 14.3.4.1(a). Treatments to summarize are the following: Placebo, ETVAX 1/4 Dose, ETVAX (highest safe dose) + 2.5 μ g dmLT, ETVAX (highest safe dose) + 5 μ g dmLT, ETVAX (highest safe dose) + 10 μ g dmLT

TABLE 14.3.4.1c:

Laboratory Results by Parameter, Maximum Severity, Study Day, and Treatment Group - Young Children (12 - 23 Months)

Programming Note: Use the same Table shell as Table 14.3.4.1(a). Treatments to summarize are the following: Placebo, ETVAX 1/4 Dose, ETVAX (highest safe dose) + 2.5 µg dmLT, ETVAX (highest safe dose) + 5 µg dmLT

TABLE 14.3.4.1d:

Laboratory Results by Parameter, Maximum Severity, Study Day, and Treatment Group - Infants (6 - 11 Months)

Programming Note: Use the same Table shell as Table 14.3.4.1(a). Treatments to summarize are the following: Placebo, ETVAX 1/8 Dose, ETVAX 1/4 Dose, ETVAX (highest safe dose) + 2.5 µg dmLT, ETVAX (highest safe dose) + 5 µg dmLT

TABLE 14.3.4.2a: Summary Statistics of Laboratory Results by Parameter, Study Visit and Treatment Group - Adults

Laboratory Parameter	Time Point	Treatment Group	N	Mean	Standard Deviation	Median	25th - 75th Percentile	Min, Max
Hemoglobin (g/dL)	Baseline	Placebo	X	XX.X	XX.X	xx.x	xx.x - xx.x	xx.x, xx.x
		ETVAX Full Dose	X	XX.X	XX.X	xx.x	xx.x - xx.x	xx.x, xx.x
		ETVAX Full Dose + 10 μg dmLT	X	XX.X	XX.X	xx.x	xx.x - xx.x	xx.x, xx.x
	Day 7	Placebo	X	XX.X	XX.X	xx.x	xx.x - xx.x	xx.x, xx.x
		ETVAX Full Dose	X	XX.X	XX.X	xx.x	xx.x - xx.x	XX.X, XX.X
		ETVAX Full Dose + 10 μg dmLT	X	XX.X	XX.X	xx.x	xx.x - xx.x	xx.x, xx.x
	Day 7, Change from Baseline	Placebo	X	XX.X	XX.X	xx.x	xx.x - xx.x	xx.x, xx.x
		ETVAX Full Dose	X	XX.X	XX.X	xx.x	xx.x - xx.x	xx.x, xx.x
		ETVAX Full Dose + 10 μg dmLT	Х	xx.x	XX.X	XX.X	XX.X - XX.X	xx.x, xx.x
Platelet Count (10 ⁹ /L)	Baseline	Placebo	X	xx.x	XX.X	XX.X	xx.x - xx.x	xx.x, xx.x
		ETVAX Full Dose	Х	XX.X	XX.X	xx.x	xx.x - xx.x	xx.x, xx.x
		ETVAX Full Dose + 10 μg dmLT	Х	XX.X	XX.X	xx.x	xx.x - xx.x	xx.x, xx.x
	Day 7	Placebo	Х	xx.x	XX.X	xx.x	xx.x - xx.x	xx.x, xx.x
		ETVAX Full Dose	Х	xx.x	XX.X	xx.x	xx.x - xx.x	xx.x, xx.x
		ETVAX Full Dose + 10 μg dmLT	X	XX.X	XX.X	xx.x	xx.x - xx.x	XX.X, XX.X
	Day 7, Change from Baseline	Placebo	X	XX.X	XX.X	xx.x	xx.x - xx.x	xx.x, xx.x
		ETVAX Full Dose	X	XX.X	XX.X	xx.x	xx.x - xx.x	XX.X, XX.X
		ETVAX Full Dose + 10 μg dmLT	X	XX.X	XX.X	xx.x	xx.x - xx.x	xx.x, xx.x

Note: Continue for all laboratory tests: White Blood Cells (10⁹/L), ALT (U/L), Creatinine (µmol/L).

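### Neutrophil and lymphocyte counts, named safety variables measured at Screening and Day 7, have no planned by-arm laboratory summary because a toxicity-grade condition is carried over to outputs that need no grade

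*SAP*

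**What the plan says.** Section 4.5.1 of the SAP lists the clinical safety laboratory measurements. Among them are "differentials (neutrophils and lymphocytes), alanine aminotransferase (ALT), albumin, total bilirubin and serum creatinine".

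Section 9.4 sets the schedule: "Safety clinical laboratory evaluations will be performed at Screening and at Day 7 at the designated site laboratory and will include" hemoglobin, followed by "white blood cells (WBC), platelet counts, neutrophils, lymphocytes, alanine transaminase (ALT), and creatinine". Albumin and total bilirubin are taken at Screening only.

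The same section then fixes what is summarised: "The summary tables will include all laboratories collected at Screening and Day 7 and which have toxicity grades". It continues: "These include HGB, platelet counts, WBC, ALT, and creatinine". The outputs described next are:

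- Tables 14.3.4.1, the distribution by severity.
- Tables 14.3.4.2, of which it says "The observed and change from screening measurements will be summarized using descriptive statistics".
- Figures 14.3.4.3, box plots of changes in laboratory values.
- Tables 14.3.4.4, results of Grade 1 or higher.

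The Table 14.3.4.2a shell shows hemoglobin and platelets and ends with a note that begins "Note: Continue for all laboratory tests: White Blood Cells" and adds ALT and creatinine. The note under Figure 14.3.4.3a continues with platelets, WBC, ALT and creatinine. Neutrophils and lymphocytes have columns only in the individual hematology listing, 16.2.8.1.

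**The concern.** A toxicity grade is needed to fill severity columns or to decide whether a result is Grade 1 or higher. It plays no part in a mean, a quartile, a change from Screening or a box plot. Section 9.4 nevertheless states one grade condition for the summary tables as a whole, and the shell for the ungraded statistics follows it. The SAP gives no reason for applying the condition there.

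The result also sits badly with section 6.1, which says without qualification that continuous variables will be summarised with descriptive statistics. Listing 16.2.8.1 carries both counts as absolute values in 10^9/L, so they are continuous.

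At stake is the descriptive safety picture in a trial whose primary objective is safety and tolerability. Total WBC does not stand in for its components, because a rise in one and a fall in the other can cancel. With 15 or 30 vaccinees per dose group (section 5), a modest shift is easier to see in a by-arm distribution than by reading listings.

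**Working it through.** The SAP gives no figure to reproduce here. The check sets the analytes measured beside the outputs planned.

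**Analytes measured at both visits (section 9.4).** Hemoglobin, WBC, platelets, neutrophils, lymphocytes, ALT, creatinine: 7.

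**Analytes named by the summary rule (section 9.4).** Hemoglobin, platelets, WBC, ALT, creatinine: 5.

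**Not summarised.** 7 − 5 = 2, neutrophils and lymphocytes; 2/7 = 29%.

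**Output by output:**

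| Output | Needs a grade? | Analytes carried |
|---|---|---|
| Tables 14.3.4.1 (severity) | Yes | The five, plus an any-parameter panel |
| Tables 14.3.4.2 (observed and change) | No | The five |
| Figures 14.3.4.3 (box plots) | No | The programming note adds no analyte outside the five |
| Tables 14.3.4.4 (Grade 1 or higher) | Yes | Graded results only |
| Listings 16.2.8.1 (individual hematology) | No | Include neutrophils and lymphocytes, with treatment group |

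The grade condition has a technical reason in the first and fourth rows. It has none in the second and third.

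The two omissions have different sources. The quoted rule speaks of summary tables, so it accounts for Tables 14.3.4.2. For the figures, section 9.4 refers to each laboratory parameter, and the omission comes from the programming note under Figure 14.3.4.3a. Both places therefore need correction.

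**Volume of data.** Planned enrolment (section 4.3) is 45 + 150 + 100 + 200 = 495. Two visits each give 495 × 2 = 990 differential results. This is a planned maximum. The footnote to Table 14.3.1.6.1 gives n=5 full-dose recipients, against 15 planned vaccinees in the full-dose toddler cohort, so the number available may be smaller. The count of two analytes out of seven does not depend on enrolment.

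**The case against.** The strongest reply is that this is an explicit choice. Section 9.4 states the rule, names the five analytes, and the shells follow it. Naming a variable as assessed does not promise a summary table: albumin and total bilirubin are also named in section 4.5.1 and get none. The primary endpoints in section 3.2.1 are proportions of SAEs, AEs and reactogenicity events, not mean laboratory changes, and the SAP cites no hematological signal for ETVAX or dmLT.

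Part of this stands. The omission is deliberate in form and touches no endpoint. But the stated basis, the existence of grades, justifies only the graded outputs. The comparison with albumin and bilirubin fails because those are collected at Screening only and can have no change from Screening.

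A second reply is that the counts are not lost, and this stands in full. A reader might infer that the trial cannot report these counts by arm, or that they vanish from every table. The SAP does not support either reading:

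- Listings 16.2.8.1 carry treatment group, visit day and both absolute counts.
- Section 4.5.1.2 makes a laboratory change that the investigator considers clinically significant an adverse event, so it would enter the by-arm tables of section 9.1.2.
- Section 1 allows deviations from the SAP to be described and justified in the study report, so a summary could still be added.

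A third reply is that grading criteria sit in Appendix II of the protocol, which the SAP does not reproduce, and that the five may be examples rather than a closed list. Every shell is built on the same five. If the two counts are in fact graded, the shells break the SAP's own rule and need correction anyway.

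**Conclusion.** The point holds in limited form. Two of the seven analytes measured at Screening and Day 7, both named as safety variables, have no planned by-arm laboratory table or figure, because a condition suited to graded outputs was carried over to ungraded ones. What is missing is the planned by-arm description of neutrophil and lymphocyte shifts that are not reported as adverse events. No estimate is biased, and no endpoint, test or decision rule changes.

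The conclusion rests on reading the five named analytes as the full set, which the shells bear out. It does not depend on whether the two counts have grades in the protocol. The change should be made because the data are already collected, safety is the primary objective and the correction is small.

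**What to change.** 1. In section 9.4, confine the toxicity-grade condition to Tables 14.3.4.1(a)-(d) and 14.3.4.4(a)-(d).
2. In Tables 14.3.4.2(a)-(d), summarise all seven analytes collected at Screening and Day 7, adding absolute neutrophil and lymphocyte counts, observed and change from Screening, by treatment group.
3. Add both counts to Figures 14.3.4.3(a)-(d).
4. Correct the notes under Table 14.3.4.2a and Figure 14.3.4.3a so that their lists match.

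The cost is SAP wording and two more parameters in existing programs, with no new data. The downside is a few more descriptive pages in an already long set of outputs.
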